2.6 Analysis of secondary objective(s)

The secondary objectives are to assess the overall response rate (ORR), CR/mCR rate, duration of CR, time to CR/mCR, duration of response, duration of CR/mCR, overall survival (OS), event free survival (EFS), progression free survival (PFS), leukemia free survival (LFS), RBC/platelets transfusion independence, changes from baseline in fatigue, pharmacokinetic, immunogenicity and safety.

2.6.1 Efficacy

2.6.1.1 Safety run-in (Part 1)

CR+mCR and overall response (ORR) rates

CR+mCR rate is defined as the proportion of participants with best overall response of either complete remission (CR) or marrow complete remission as per investigator assessment. CR/mCR rate will be provided with exact 95% confidence interval (Clopper and Pearson 1934).

ORR rate is defined as the proportion of participants with best overall response of hematological improvement (HI) or better as per investigator assessment. ORR rate will be provided with exact 95% confidence interval (Clopper CJ and Pearson ES 1934). CR/mCR and ORR will be provided by dose level of sabatolimab.

Improvement of RBC/platelets transfusion independence

RBC/Platelets transfusion independence rate is defined as the proportion of participants having received no RBC/Platelets transfusions during at least 8 consecutive weeks after start of treatment. The number and percentage of participants will be shown for the FAS and then also in only those with transfusion dependence at baseline. Percentages will be provided with exact 95% confidence interval (Clopper and Pearson 1934). Shift tables will be provided to describe the transfusion status at baseline versus the best transfusion status postbaseline.

For participants with at least one period of transfusion independence post-baseline, the total duration of all transfusion independence periods (which all individually must be at least 8 weeks) will be also summarized. The duration of each period of transfusion independence is defined from the end date of the last transfusion received until the date transfusions are given again or last date of treatment administration in case transfusions had not (re-)started during treatment.

The total duration of all transfusion independence periods is the sum of each period of the transfusion independence. The data will be summarized by dose level of sabatolimab.

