Response assessment will be performed by investigator according to the assessment schedule depicted in Table 8-1. Moreover, participants can be assessed for disease response (bone marrow assessment, hematology, transfusion) at any time if clinically indicated as an example if there is a clinical suspicion of progression/relapse, in particular after a participant has achieved a CR.

Bone marrow assessments will be performed at screening and pre-dose on C3D1. From C7D1, bone marrow assessments will be performed every 3 cycles until C13D1 (C7D1, C10D1, C13D1), then every 6 cycles until C25D1 (C19D1 and C25D1) and thereafter every 12 cycles (C37D1, C49D1 etc.) and as clinically indicated during the treatment period.

Hematology assessments will be performed at screening, pre-dose on D1, D8 and D22 of Cycles 1 and 2, and thereafter pre-dose on D1 and D8 of each cycle until end of treatment.

Bone marrow and peripheral blood pathology specimens (i.e. bone marrow aspirate slides, bone marrow biopsy block if applicable, peripheral blood smears) prepared locally for the disease response assessment, should be sent to the Novartis designated central laboratory for storage. This includes specimens taken during the regular work-up of the participant and used as baseline assessment for the study as mentioned in Section 8.2. A copy of the corresponding pathology reports should be collected and sent to the Novartis designated central laboratory for storage. Central morphology review of the pathology specimens may be performed, if deemed necessary. For China only: Storage of the above pathology specimens and reports in a Novartis designated laboratory will be performed, if adequate approval has been obtained from all relevant Chinese authorities.

Participants who discontinue treatment for reasons other than documented disease progression, death, lost to follow-up, or withdrawal of consent, will enter the efficacy follow-up phase.

In the efficacy follow-up phase, hematology assessments must continue to be performed every 3 months, response should be assessed at least every 12 months, and bone marrow assessment should be done at least every 12 months thereafter per Table 8-1, or as clinically indicated any time in case disease progression is suspected. Further information about blood transfusions will be continuously collected throughout the efficacy follow-up period.

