OS is defined as the time from start date of treatment to date of death due to any cause. If a participant is not known to have died, then OS will be censored at the latest date the participant was known to be alive (on or before the cut-off date). All deaths will be taken into account whenever the death occurred, i.e. even after new anti-neoplastic therapy, HSCT, interruptions, or discontinuation of study treatment due to any reason.

OS will be estimated using the Kaplan-Meier method. The median OS along with 95% confidence interval will be presented.

Improvement of RBC/platelets transfusion independence

Red blood cells (RBC)/Platelets transfusion independence rate is defined as the proportion of participants having received no RBC/Platelets transfusions during at least 8 consecutive weeks (see Section 8.3.1 for details).

The number and percentage of participants will be shown for the overall FAS and then also in only those with transfusion dependence at baseline (i.e \geq 3 units of transfusion within 8 consecutive weeks prior to start of treatment).

Percentages will be provided with exact 95% confidence intervals (Clopper CJ and Pearson ES 1934). For participants with at least one period of transfusion independence, the total duration of all transfusion independence periods will be also summarized.

The duration of the transfusion independence is defined from the end date of the last transfusion received until the date transfusions are given again or last treatment in case transfusions had not (re-)started during treatment.

Immunogenicity analysis

Immunogenicity will be characterized descriptively by tabulating ADA prevalence at baseline and ADA incidence on-treatment.

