2.1 Data analysis / general information

The primary analysis, as well as the analyses that will be used for the safety review meetings of the safety run-in part of the study will be performed by Novartis. SAS or R will be used to perform all data analyses and to generate tables, figures and listings.

As Novartis decided to halt enrollment of the expansion part of the study in September 2022, the study data will be analyzed and reported based on all data up to DBL in an abbreviated final Clinical Study Report (CSR).

Data included in the analysis / data cut-off handling

For each of the safety review meetings a data cut-off date will be established after the targeted number of evaluable participants have completed 2 cycles of treatment. All safety data (including duration of exposure to study drugs, dose interruptions/reductions, study drug discontinuation, etc.), demographics, disease history, hematology data, blast counts from bone marrow and PK data with an assessment date or event start date (e.g. laboratory assessment date or start date of an adverse event) prior to or on the cut-off date will be included in the analysis. The list of analyses to be presented at the time of the safety review meetings are provided in Section 2.8.

For the abbreviated CSR, all data collected prior to DBL will be included in the analysis.

General analysis conventions

Qualitative data (e.g. gender, race) will be summarized by means of contingency tables; a missing category will be included as applicable. Percentages will be calculated using the number of participants in the relevant population or subgroup as the denominator.

Quantitative data (e.g. age, body weight) will be summarized by appropriate descriptive statistics (e.g. mean, standard deviation, median, 25th and 75th percentiles, minimum, and maximum).

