RBC/Platelets transfusion independence rate is defined as the proportion of participants having received no RBC/Platelets transfusions during at least 8 consecutive weeks after start of treatment. The number and percentage of participants will be shown for the FAS and then also in only those with transfusion dependence at baseline. Percentages will be provided with exact 95% confidence interval (Clopper and Pearson 1934). Shift tables will be provided to describe the transfusion status at baseline versus the best transfusion status postbaseline.

For participants with at least one period of transfusion independence post-baseline, the total duration of all transfusion independence periods (which all individually must be at least 8 weeks) will be also summarized. The duration of each period of transfusion independence is defined from the end date of the last transfusion received until the date transfusions are given again or last date of treatment administration in case transfusions had not (re-)started during treatment.

The total duration of all transfusion independence periods is the sum of each period of the transfusion independence.

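### Transfusion-independence periods still running at the last dose are closed at that date and summarised as complete, so an ongoing period can only be understated, and the cut conflicts with the 8-week rule used for the rate

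*SAP*

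**What the plan says.** Protocol Table 2-1 and SAP Table 1-1 list the proportion of participants who become transfusion independent, and the duration of that independence, as a secondary endpoint. SAP 1.2 drops only the fatigue endpoint from the abbreviated report, so this one will be presented.

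- **End of a period.** SAP 2.6.1.1, repeated in 2.6.1.2, starts a period at the end of the last transfusion and runs it to the next transfusion or to the "last date of treatment administration in case transfusions had not (re-)started during treatment". Protocol 12.5.1.1 and 12.5.1.2 have the same rule: "or last treatment in case transfusions had not (re-)started during treatment".
- **Combination.** The SAP requires each period to last at least 8 weeks and then adds them up: "The total duration of all transfusion independence periods is the sum of each period of the transfusion independence". The totals are to be summarised. SAP 2.1 says that quantitative data "will be summarized by appropriate descriptive statistics", with mean and median among the examples.
- **Censoring.** None is specified. SAP 2.6.1.2 names the time-to-event endpoints whose individual times and event or censoring types are listed. Duration of CR, of CR/mCR and of response are on that list; duration of transfusion independence is not.
- **Rate.** SAP 2.6.1.1 counts a participant with at least 8 consecutive transfusion-free weeks after the start of treatment. The transfusion-status definitions under SAP Table 2-2 allow any 8 weeks in the course of the study. Neither stops at the last dose.
- **Data after the last dose.** Protocol 8.3.1 states: "Further information about blood transfusions will be continuously collected throughout the efficacy follow-up period". A footnote to Protocol Table 8-1 has these transfusions entered every 12 weeks.

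**The concern.** A period with no transfusion before the last dose has not been seen to end. Closing it at the last dosing date and entering it as a finished duration mixes two things: how long independence lasted, and how long the participant was dosed. Three groups are affected: participants still on treatment and transfusion-free at database lock; those who stop treatment transfusion-free and stay so; and those who are transfused only after stopping, whose true end date may be in the database but is not used.

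The rate and the duration also use different windows. A participant can enter the numerator of the rate and contribute no qualifying period to the duration summary, and the SAP does not say what happens then.

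At stake is whether a reported duration of transfusion independence means what its label says. Recruitment stopped after the run-in and the report uses data up to database lock, so some unfinished periods are to be expected; the documents do not show how many.

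**Working it through.** The documents give no figure for this endpoint, so there is nothing to reproduce.

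**1. Direction for one period.** Let T be the true length of a period and C the time from its start to the last dose. If a transfusion restarts during treatment, the recorded value is T. If not, it is C, and C ≤ T. The recorded value is min(T, C), which never exceeds T. This needs no distributional assumption.

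**2. Conflict with the rate.** Take a last transfusion on Day 10 and a last dose on Day 42 (venetoclax Day 14 of Cycle 2: 28 + 14 = 42). The participant then stays transfusion-free to Day 120 with no new therapy.
- Rate: 120 − 10 = 110 days, at least 56, so counted as independent.
- Duration: 42 − 10 = 32 days, under 56, so no qualifying period.

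**3. Small loss even in a completed final cycle.** If the last dose is venetoclax on Day 14, the cut falls 28 − 14 = 14 days before the cycle ends. If only sabatolimab on Day 8 is given, it falls 28 − 8 = 20 days before.

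**4. How far the size depends on assumptions.** Nothing below is an estimate for this trial.

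*Exponential T and C, independent, periods of at least 56 days kept.* The minimum is 56 / 30.4375 = 1.84 months. Assume a median T of 12 months and a median C of 8 months.
- True median: 12 + 1.84 = 13.8. True mean: 12 / ln 2 + 1.84 = 19.2.
- Median of min(T, C): 1 / (1/12 + 1/8) = 4.8, so the recorded median is 4.8 + 1.84 = 6.6 and the recorded mean is 4.8 / ln 2 + 1.84 = 8.8.
- Share of periods cut: (1/8) / (1/12 + 1/8) = 60%.

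The shortfall of the mean in the two extreme cases tried:

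| Median T, C (months) | True mean | Recorded mean | Shortfall |
|---|---|---|---|
| 6, 16 | 10.5 | 8.1 | 22% |
| 24, 4 | 36.5 | 6.8 | 81% |

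*Correlated T and C (12 and 8 months, simulated).* The recorded mean is 10.9 against 19.2 at correlation 0.5, and 12.4 against 19.1 at 0.8. The shortfall shrinks but remains.

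*Last dose uniform over a range, periods starting 2 months after first dose (simulated medians).*

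| Median T | Last dose (months) | True median | Recorded median | Ratio |
|---|---|---|---|---|
| 12 | 6–18 | 13.8 | 7.6 | 0.55 |
| 12 | 12–24 | 13.8 | 11.5 | 0.83 |
| 6 | 6–18 | 7.8 | 6.1 | 0.78 |
| 6 | 12–24 | 7.8 | 7.8 | 1.00 |

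Over all nine combinations tried (median T of 6, 12 or 18 months; last dose at 6–12, 6–18 or 12–24 months) the ratio ran from 0.32 to 1.00.

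**5. Would Kaplan-Meier give a median here?** With 8 contributing participants, median T 12 months and censoring at a last dose at 6–18 months, a Kaplan-Meier median is reached in about half of simulated trials. With last dose at 6–12 months it is reached in about a quarter.

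**The case against.** The strongest reply is that this is an on-treatment quantity. The rule is explicit, the same in both documents, and turns on whether transfusions restart during treatment. SAP 2.4.2 also normalises transfusion units over on-treatment intervals. Because all periods are summed per participant, the comparison with duration of CR, a single-episode endpoint, is imperfect. Observed on-treatment transfusion-free time is not a biased estimate of itself. This would answer the point if either document used that label. Both call the endpoint duration of transfusion independence.

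Other parts of the reply stand and limit the point:

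- The SAP sections say only that the durations are summarised. That they will be averaged is inferred from the general convention in SAP 2.1, which gives examples.
- Kaplan-Meier output is conditional on follow-up and event numbers even for the endpoints that SAP 2.6.1.2 lists, and a median may not be reached in so small a group.
- Participants who stop for documented progression do not enter efficacy follow-up (Protocol 8.3.1). Censoring may then coincide with rising transfusion need, so Kaplan-Meier is not guaranteed to be unbiased.
- All transfusions are to be listed (SAP 2.4.2), so a careful reader could identify ongoing periods by hand. The rate, its interval and the shift tables do not use the cut.

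A reader might infer from the illustrations that the reported duration will be roughly half the truth, or that every summary statistic must be too low. The documents support neither. The distributions are assumed, and one scenario left the median unchanged. The summary also drops cut periods shorter than 8 weeks, and a period may start before the first dose; both can raise the reported values.

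**Conclusion.** The point holds as a defect of definition. Under the rule as written, an unfinished period is recorded as complete and can only be understated. This follows from the definition alone. The conflict between the rate and the duration also follows from the text, and the worked example shows that it can occur.

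The size is not computable from the documents. Any percentage rests on assumed durations and should not be quoted as the bias in this study.

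The consequence is minor. This is a descriptive secondary endpoint in an abbreviated report on a run-in planned for about 18 participants. The dual-criterion test of the CR rate will not be performed (SAP 3), and no decision rule uses this duration.

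**What to change.** In SAP 2.6.1.1 and 2.6.1.2:

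1. Flag every period not ended by a transfusion as ongoing, censored at the last date with transfusion information. Use the follow-up records, and stop at new antineoplastic therapy, HSCT or database lock. State this window once and apply the 8-week minimum over the same window for rate and duration.
2. Add duration of transfusion independence, taken as the first qualifying period, to the SAP 2.6.1.2 endpoints whose individual time and event or censoring type are listed. Produce Kaplan-Meier output only if the data permit, under the condition already stated there.
3. If the summed total is kept, label it observed on-treatment transfusion-free time and report how many periods were ongoing at the cut.

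The cost is some SAP wording and one small derivation from records already collected. The downside is that a Kaplan-Meier median may not be estimable with few participants, and censoring at progression may be informative; the report should say so. If only one change is made, the third is the minimum needed for the number to match its label.

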2.6.1.2 Cohort 2 of Safety run-in (Part 1) and Expansion (Part 2)

All time-to-event endpoints (including duration of CR, time to CR/mCR, duration of response, duration of CR/mCR, OS, EFS, PFS and LFS) will be derived and stored in analysis datasets, and the individual time and specific event / censoring type will be listed. However, the amount of available follow-up data and number of events will determine if standard KM tables and/or graphics will be produced, which will be further discussed in the TFL shell.

Novartis	
Statistical Analysis Plan	n (SAP)

Bone marrow blasts percentage will be listed. In addition, for some selected laboratory parameters and for bone marrow blasts percentage, trends over time (baseline and on-treatment timepoints during the first 6 cycles of treatment including C7D1 assessment) will be displayed via boxplots, and corresponding tables displaying the summary statistics for these selected timepoints will be produced.

CR+mCR rate

CR+mCR rate is defined as the proportion of participants treated with sabatolimab at 800 mg Q4W with best overall response of either complete remission (CR) or marrow complete remission as per investigator assessment. CR/mCR rate will be provided with exact 95% confidence interval (Clopper CJ and Pearson ES 1934). The same rules applied to the primary endpoint (i.e. CR rate) will be applied to the CR/mCR rate.

Overall Response Rate (ORR)

ORR rate is defined as the proportion of participants treated with sabatolimab at 800 mg Q4W with best overall response of hematological improvement (HI) or better as per investigator assessment. ORR rate will be provided with exact 95% confidence interval (Clopper and Pearson 1934). The same rules applied to the primary endpoint (i.e. CR rate) will be applied to CR/mCR rate.

Duration of CR

The duration of CR will be derived for participants treated with sabatolimab at 800 mg Q4W who achieve CR per modified IWG-MDS Cheson 2006 (prior to any new antineoplastic therapy, including HSCT) as per investigator assessment and is defined from the first occurrence of CR until relapse, progression, or death due to any reason. Relapse, progression or death occurring after HSCT will be considered as event for the duration of CR. The date of the event will be the date of relapse, progression, or death whichever occurs first. If participant did not relapse nor progress/die, the duration of response will be censored at the last adequate response assessment. If the participant has started a new antineoplastic therapy without prior documented relapse or progression, the duration of CR is censored at the last adequate assessment prior to the start of that therapy, and thus any subsequent relapse/progression/death will not be considered as an event for duration of CR.

Duration of CR will be estimated using the Kaplan-Meier Method. The median duration of CR along with 95% Confidence interval will be presented.

Duration of CR/mCR

The duration of CR/mCR will be derived for participants treated with sabatolimab at 800 mg Q4W who achieve CR or mCR (prior to any new antineoplastic therapy, including HSCT) as per investigator assessment and is defined from the first occurrence of CR or mCR until relapse, progression or death due to any reason. Relapse, progression or death occurring after HSCT will be considered as event for the duration of CR/mCR, the date of the event will be the date of relapse, progression, or death whichever occurs first. If the participant did not relapse, progress or die, the duration of CR/mCR will be censored at the last adequate response assessment. If the participant started a new antineoplastic therapy, without prior documented relapse or

Novartis	For business use only	Page 28 of 46
Statistical Analysis Plan (SAP)		MBG453B12203

progression, the duration of CR/mCR is censored at the last adequate assessment prior to the start of that therapy and thus any subsequent relapse/progression/death will not be considered as an event for duration of CR/mCR.

Duration of CR/mCR will be estimated using the Kaplan-Meier Method. The median duration of CR/mCR along with 95% Confidence interval will be presented.

Duration of response

The duration of response will be derived for participants treated with sabatolimab at 800 mg Q4W who achieve HI or better (prior to any new antineoplastic therapy, including HSCT) as per investigator assessment and is defined from the first occurrence of CR, mCR, PR or HI until relapse, progression or death due to any reason.

Relapse, progression or death occurring after HSCT will be considered as an event for the duration of response. The date of the event will be the date of relapse, progression, or death whichever occurs first. If the participant did not relapse, progress or die, the duration of response will be censored at the last adequate response assessment. If the participant started a new antineoplastic therapy without prior documented relapse or progression, the duration of response is censored at the last adequate assessment prior to the start of that therapy and thus any subsequent relapse, progression, or death will not be considered as an event for duration of response.

Duration of response will be estimated using the Kaplan-Meier method. The median duration of response along with 95% confidence interval will be presented.

Time to CR/mCR

The time to CR/mCR will be derived for all participants treated with sabatolimab at 800 mg Q4W and is defined from start of treatment to first occurrence of CR/mCR (prior to any new antineoplastic therapy, including HSCT). For participants who reached CR /mCR after HSCT or a new antineoplastic therapy, the time to CR/mCR will be censored at the time of HSCT or initiation of new antineoplastic therapy.

For participants who did not reach CR/mCR, a). if they did not progress, die or progress to acute myeloid leukemia either, the time to CR/mCR will be censored at the last adequate response assessment; or b). if they progressed, died or the disease progressed to acute myeloid leukemia, the time to CR/mCR will be censored at the maximum follow-up (last participant last visit).

Time to CR/mCR will be estimated using the Kaplan-Meier method. The median time to CR/mCR along with 95% confidence interval will be presented.

Event-free survival (EFS)

Event-free survival (EFS) is defined from the date of start of treatment to:

- Lack of complete remission within the maximum of first 6 months or 6 cycles (including C7D1 assessment) of start of treatment
- Progression/Relapse
- Death from any cause

Whichever occurs first.

Participants treated with sabatolimab at 800 mg Q4W who failed to achieve CR within 6 cycles of treatment will have their EFS event documented at start of treatment. If participant discontinued treatment due to any reason (including death) prior to 6 cycles and without CR will be considered as EFS event documented at start of treatment date.

Progression/Relapse, or death events after HSCT, and transfusion of blood products, will be taken into account. However, Progression/Relapse, or death, occurring after initiation of new antineoplastic therapy, will not be considered an event and EFS will be censored at the last adequate response assessment prior to the new antineoplastics therapy.

In case of two or more missing assessments prior to documented progression, relapse or death, EFS will be censored at the last adequate response assessment prior to the documentation of relapse or death.

EFS will be estimated using the Kaplan-Meier method. The median EFS along with 95% confidence interval will be presented.

Progression free survival (PFS)

PFS is defined as the time from start date of treatment to date of relapse, progression (including transformation to acute leukemia per WHO 2016 classification) or death due to any cause. If a participant is not known to have relapsed, progressed nor died, then PFS will be censored at the last adequate response assessment (on or before the cut-off date). Progression/relapse or death occurring after a). HSCT, b). interruptions or c). discontinuation of study treatment due to any reason will be taken into account. However, Progression/Relapse, death occurring after initiation of new antineoplastic therapy will not be considered an event and PFS will be censored at the last adequate response assessment.

In case of two or more missing assessments prior to documented progression, relapse or death, PFS will be censored at the last adequate response assessment prior to the documentation of progression, relapse or death.

PFS will be estimated using the Kaplan-Meier method. The median PFS along with 95% confidence interval will be presented.

Leukemia Free survival (LFS)

LFS is defined as the time from start of treatment to transformation to acute leukemia as per investigator assessment defined as the following:

- \geq 20% blasts in bone marrow/ peripheral blood (per WHO 2016 classification)
- Diagnosis of extramedullary acute leukemia
- Death due to any cause

whichever occurs first.

If a participant is known to not have progressed to leukemia as defined by the criteria mentioned above, then LFS will be censored at the last bone marrow/peripheral blood assessments (on or before the cut-off date). Any of the three events (i.e. $\geq 20\%$ blasts in bone marrow/peripheral blood, diagnosis of extramedullary acute leukemia or death) occurring after HSCT, interruptions, or discontinuation of study treatment due to any reason will be taken into account. However, events occurring after initiation of new antineoplastic therapy will not be considered

an event and LFS will be censored at the last adequate assessment of bone marrow and/or peripheral blood, or diagnosis of extramedullary acute leukemia prior to initiation of new antineoplastic therapy.

In case of two or more missing assessments prior to documented progression to leukemia, LFS will be censored at the last adequate assessment (bone marrow and/or hematology assessment) prior to the documentation of progression to leukemia.

LFS will be estimated using the Kaplan-Meier method. The median LFS along with 95% confidence interval will be presented.

Overall Survival (OS)

OS is defined as the time from start date of treatment to date of death due to any cause. If a participant is not known to have died, then OS will be censored at the latest date the participant was known to be alive (on or before the cut-off date). All deaths will be taken into account whenever the death occurred, i.e. even after new anti-neoplastic therapy, HSCT, interruptions, or discontinuation of study treatment due to any reason.

The OS censoring reason will be summarized as 'Alive' or 'Lost to follow-up'. Participants not known to have died will have the censoring reason 'Lost to follow-up' if the reason for discontinuation from study is 'Lost to follow-up' or 'Withdrawal of consent'. Otherwise, participants will have the censoring reason 'Alive'.

OS will be estimated using the Kaplan-Meier method. The median OS along with 95% confidence interval will be presented.

Improvement of RBC/platelets transfusion independence

RBC/Platelets transfusion independence rate is defined as the proportion of participants having received no RBC/Platelets transfusions during at least 8 consecutive weeks after start of treatment. The number and percentage of participants will be shown for the FAS and then also in only those with transfusion dependence at baseline. Percentages will be provided with exact 95% confidence interval (Clopper and Pearson 1934). Shift tables will be provided to describe the transfusion status at baseline versus the best transfusion status postbaseline.

For participants with at least one period of transfusion independence post-baseline, the total duration of all transfusion independence periods (which all individually must be at least 8 weeks) will be also summarized. The duration of each period of transfusion independence is defined from the end date of the last transfusion received until the date transfusions are given again or last date of treatment administration in case transfusions had not (re-)started during treatment.

The total duration of all transfusion independence periods is the sum of each period of the transfusion independence.

